#### **8.4 Subject Replacement**

Up to 2 replacement subjects per cohort may be enrolled into Part 1 (SAD). The maximum number of subjects that may be dosed is 50.

Up to 3 replacement subjects per cohort may be enrolled into Part 2 (MAD). The maximum number of subjects that may be dosed is 60.

Any subject withdrawn due to an IMP-related AE will not be replaced. Subjects withdrawing for other reasons may be replaced as required by agreement between the investigator and Sponsor to ensure sufficient evaluable subjects.

#### **8.5 Stopping Criteria**

The study will be halted, and the risk to other subjects evaluated, if any of the following criteria are met:

- A serious adverse reaction (i.e., a SAE considered at least possibly related to the test product) in one subject
- Severe adverse reactions (i.e., severe AEs considered as at least possibly related to the test product) in two subjects in the same cohort, within the same system organ class.
- There is evidence of drug-induced liver injury in any subject:
  - ALT or aspartate aminotransferase (AST)  $>3 \times$  upper limit of normal (ULN) and total bilirubin  $>2 \times$  ULN or INR  $>1.5$  with no alternative etiology OR
  - ALT or AST  $>3$  ULN with fatigue, nausea, vomiting, right upper quadrant (RUQ) pain/tenderness, fever, rash and/or eosinophilia with no alternative etiology OR
  - ALT or AST  $>8 \times$  ULN with no alternative etiology

Relatedness to IMP will be determined by the investigator.

The IRB will be notified if the study is halted. The study may be resumed or terminated; however, it will not be resumed until a further notice to resume the study is submitted and approved by the IRB.

Also see the pharmacodynamic criteria to cap dose escalation in SAD or MAD in the Pharmacodynamic Rationale [Section 6.4](#).

## 8.6 Study Termination

The study may be terminated by the Sponsor at any time. Notification of termination must be provided to the IRB as soon as possible, clearly explaining the reasons for termination. A description of follow-up measures taken for safety reasons, if applicable, should also be provided.

If the study is abandoned prior to commencement of any protocol activities, the investigator must notify the IRB outlining the reasons for abandonment of the trial.

The study will be completed as planned unless there is a need for temporary suspension or early termination of the study secondary to any of the following:

- Occurrence of stopping events otherwise defined in this protocol.
- New information regarding the safety of the IMP that indicates that the risk/benefit profile is no longer acceptable.
- Significant violation of Good Clinical Practice (GCP) that compromises subject safety or the ability to achieve the primary study objectives.

If any of the above occur the study will be terminated if careful review of the overall risk/benefit analysis described in [Section 6.6](#) demonstrates that the assumptions have changed and that the overall balance is no longer acceptable. The IRB will be informed of study termination.

If it becomes necessary to consider termination of the study, dosing may be suspended pending discussion between the investigator and Sponsor.

The study may be terminated or suspended at the request of the IRB.

## 8.7 Lost to Follow-Up

A subject will be considered lost to follow-up if they fail to return for scheduled visits and cannot be contacted by the clinical unit.

If a subject fails to return to the clinical unit for a required study visit:

- The clinical unit must attempt to contact the subject and reschedule the missed visit as soon as possible
- The investigator or designee must make every effort to regain contact with the participant (e.g., three telephone calls and, if necessary, a certified letter to the participant's last known mailing address or local equivalent methods). These contact attempts should be documented in the subjects' electronic case report form (eCRF)
- If the subject cannot be contacted, they will be considered lost to follow-up

## 8.8 Subject Selection List and Randomization

This is a double-blind, randomized, placebo-controlled study; therefore, a randomization schedule will be produced for each study part.

A subject selection list will be produced for each study part prior to dosing using the randomization schedule and will be retained in the Investigative Site File (ISF).

In Part 1, for sentinel dosing, a group of 2 subjects will be dosed ahead of the remaining subjects in each cohort. A randomization schedule will be used such that the first 2 subject numbers will be allocated to active or placebo in a 1:1 ratio (i.e., 1 subject will be randomly assigned to receive PDM608 and 1 subject will be randomly assigned to receive matching placebo). The remaining 6 subject numbers will be allocated to active or placebo in a 5:1 ratio (i.e., 5 subjects will be randomly assigned to receive PDM608 and 1 subject will be randomly assigned to receive matching placebo).

For Part 2, a randomization schedule will be used to allocate subject numbers to PDM608 or placebo in a 3:1 ratio (i.e., in each cohort, 9 subjects will be randomly assigned to receive PDM608 and 3 subjects will be randomly assigned to receive matching placebo).

Subjects will be randomized prior to administration of the first dose.

#### **8.8.1 Subject Numbers**

Four-digit subject numbers will be allocated prior to initial dosing according to a code established by Quotient. Replacement subjects will be allocated subject numbers where the last three digits are the same as those of the original subject (e.g., if Subject 1005 withdraws, the replacement will have Subject Number 9005 and will receive the same regimen as Subject 1005).

#### **8.8.2 Blinding**

This is a double-blind study; treatment assignment will not be known to the subjects, the Sponsor or the staff involved in the clinical evaluation of the subjects and the analysis of data. The randomization schedule and disclosure envelopes will be generated by an unblinded statistician at Quotient according to Quotient's SOPs. The unblinded statistician will not be involved in any decisions relating to populations for analysis prior to unblinding. Prior to database lock and unblinding, all original randomization materials including the original final signed and dated randomization schedule will be held by the Quality Assurance (QA) department at Quotient. The Data Sciences department will not have access to the randomization schedule before database lock and unblinding.

Interim PK parameter estimations will be performed using bioanalytical data applied with subject aliases to maintain blinding.

There may be instances where interim data have the potential to reveal treatment (e.g., missed blood sampling occasions). In these cases, every effort will be made by the unblinded pharmacokineticist to maintain blinding by appropriate presentation of data to the study team. Data demonstrating extremes of exposure will always be presented regardless of the potential to break blinding. To permit selection of the appropriate dose, individual data if judged necessary will be presented to the review committee, regardless of the potential to reveal blinding.

The unblinded Pharmacist or designee at the clinical site will receive a copy of the final randomization schedule for preparation of the study drug and preparation of the subject selection list. A copy of the randomization schedule will also be made available to the laboratory performing the bioanalysis to allow selective analysis of drug concentrations and to the pharmacovigilance provider for analysis of pharmacovigilance.

Two sets of disclosure envelopes (i.e., sealed envelopes containing individual subject randomization details) will be provided. One set will be held in the clinical area and the other retained in the ISF. These may be used in the event of an emergency by the investigator. Any request for information on the randomization schedule after initial issue must be made using a randomization disclosure form to the designee of the randomization except in the case of emergency unblinding, which must be recorded on the emergency unblinding form including details of timing, those unblinded and scope of unblinding. Access to study drug assignment will be immediately available if the investigator deems it necessary to break blinding in the interest of a subject's medical safety, in case of a medical emergency or if warranted during scheduled safety reviews. The medical monitor must be contacted within 24 hours following disclosure of study drug assignment.

Details of any disclosure of the randomization schedule will be documented and retained in the ISF. The Sponsor will be notified if blinding is broken.

For each individual study part blinding will be broken after the study database has been locked and the safety and necessary populations have been defined.

## **9 Selection of Subjects**

### **9.1 Informed Consent**

The investigator or delegated, qualified study staff member will explain and review the IRB approved informed consent form (ICF) with each subject. Subjects will then be given the opportunity to ask questions and will be informed of their right to withdraw from the study without prejudice. After this explanation and before any study specific procedures are performed the subject will voluntarily sign and date the IRB approved ICF.

### **9.2 Inclusion Criteria**

#### **Informed Consent and Compliance**

1. Must be able to understand a written informed consent, which must be obtained prior to initiation of study procedures
2. Must be willing and able to comply with all study requirements

#### **Demographics and Contraception**

3. Aged 18 to 65 years inclusive at time of signing informed consent
4. Must agree to use an adequate method of contraception (as defined in [Section 9.4](#))

#### **Baseline Characteristics**

5. Healthy men or non-pregnant, non-lactating healthy women of non-childbearing potential
6. Body mass index (BMI) of 18.0 to 33.0 kg/m^2 as measured at screening
7. Weight ≤100 kg at screening

Inclusion criterion 5 from the list above will be re-assessed at admission/pre-dose on Day 1.

### **9.3 Exclusion Criteria**

#### **Medical/Surgical History and Mental Health**

1. Serious adverse reaction or serious hypersensitivity to any drug or the formulation excipients
2. Presence or history of clinically significant allergy requiring treatment as judged by the investigator. Hay fever is allowed unless it is active
3. Significant serious skin disease, including rash, food allergy, eczema, psoriasis or urticaria
4. History of clinically significant autoimmune, cardiovascular, renal, hepatic, chronic respiratory or GI disease (except cholecystectomy), neurological or psychiatric disorder, illness/infection/hospitalization or surgical procedure within 30 days prior to first dose of study drug or any uncontrolled medical illness as judged by the investigator

#### **Physical Examination**

5. Have poor venous access that limits phlebotomy

#### **Diagnostic Assessments**

6. Evidence of current SARS-CoV-2 infection or exposure to confirmed infection within 10 days prior to the first dose of study drug
7. Clinically significant abnormal clinical chemistry, hematology or urinalysis as judged by the investigator (laboratory parameters are listed in [Appendix 1](#)). Subjects with Gilbert's Syndrome are allowed
8. Positive hepatitis B surface antigen (HBsAg), hepatitis C virus antibody (HCV Ab), human immunodeficiency virus (HIV) antibody results or positive tuberculosis (TB) screening test
9. Evidence of renal impairment at screening, as indicated by an estimated creatinine clearance (CLcr) of <90 mL/min using the Cockcroft-Gault equation
10. Subjects with a QTcF interval of >450 msec at screening or first admission. At screening, QTcF will be based on a single 12-lead ECG; this single ECG can be repeated once if parameters are outside the limits for confirmation. At admission, this value will be from the mean of triplicate values
11. Positive highly sensitive serum pregnancy test at screening or highly sensitive urine pregnancy test at first admission. Those who are pregnant or lactating will be excluded

#### **Prior Study Participation**

12. Subjects who have received any IMP in a clinical research study within 5 half-lives or within 30 days prior to first dose (whichever is longer)

13. Subjects who have previously been administered IMP in this study. Subjects who have taken part in Part 1 are not permitted to take part in Part 2

**Prior and Concomitant Medication**

14. Subjects who are known to have received an antibody (as a treatment or as a participant in another study) may be eligible to participate after review by Investigator and/or Sponsor, to limit subjects who may have baseline anti-human antibodies
15. Subjects who are taking, or have taken, any prescribed or over-the-counter drug or herbal remedies (other than up to 4 g per day acetaminophen and HRT) in the 14 days or 5 half-lives (whichever is longer) before IMP administration (see [Section 11.3](#)). Exceptions may apply on a case-by-case basis if considered not to interfere with the objectives of the study as determined by the investigator
16. Subjects who have had a COVID-19 vaccine within 14 days prior to first dose or have a COVID-19 vaccine scheduled between their first dose of IMP and anticipated final study visit

**Lifestyle Characteristics**

17. History of any drug or alcohol abuse in the past 2 years, as determined by the Investigator according to the definitions of alcohol use disorder and substance abuse disorder in the Diagnostic and Statistical Manual (DSM)-5
18. Regular alcohol consumption in men >21 units per week and women >14 units per week (1 unit = 12 oz 1 bottle/can of beer, 1 oz 40% spirit or 5 oz glass of wine)
19. A confirmed positive alcohol urine test at screening or first admission
20. Current smokers and those who have smoked within the last 12 months or a confirmed positive urine cotinine test at screening or first admission
21. Current users of e-cigarettes and nicotine replacement products and those who have used these products within the last 12 months
22. Positive drugs of abuse test result (drugs of abuse tests are listed in [Appendix 1](#))

**Other**

23. Men with pregnant or lactating partners
24. Donation of blood for transfusion within 2 months or donation of plasma within 7 days prior to first dose of study medication
25. Subjects who are, or are immediate family members of, a study site or Sponsor employee
26. Failure to satisfy the investigator of fitness to participate for any other reason

Exclusion criteria [6](#), [7](#), [10](#), [11](#), [12](#), 14, 16, 19, 20, 21, 22, 23, 24 and 26 from the list above will be re-assessed at admission/pre-dose on Day 1.

Healthy subjects who do not meet the inclusion/exclusion criteria for the study will not be enrolled.

## 9.4 Contraception and Restrictions

### Men with Partners of Childbearing Potential

Men who are sexually active with a partner of childbearing potential must use, with their partner, a condom plus an approved method of highly effective contraception from the time of informed consent until 175 days after last IMP administration.

The following methods are acceptable:

- Partner's use of combined (estrogen and progestogen-containing) hormonal contraception associated with inhibition of ovulation:
  - oral
  - intravaginal
  - transdermal
- Partner's use of progestogen-only hormonal contraception associated with inhibition of ovulation:
  - oral
  - injectable/implantable
  - intrauterine hormone-releasing system
- Partner's use of intrauterine device
- Vasectomized
- Partner's bilateral tubal occlusion

### Men with Partners of Non-childbearing Potential

There is an unknown risk of drug exposure through ejaculate (which also applies to vasectomized men) that might be harmful to sexual partners. Therefore, even if a man is sexually active with a partner of non-childbearing potential they will be required to use a condom from the time of informed consent until 175 days after last IMP administration (approximately 2.5 sperm turnover rate).

### All Men

Sexual abstinence is considered a highly effective method only if defined as refraining from heterosexual intercourse during the entire period of risk associated with the study treatments. The reliability of sexual abstinence needs to be evaluated in relation to the duration of the clinical trial and the preferred and usual lifestyle of the subject.

### Women of Non-Childbearing Potential

Women who are not of childbearing potential do not need to use any methods of contraception. A woman is considered of childbearing potential (WOCBP) unless post-menopausal or permanently sterile. Permanent sterilization methods include hysterectomy, bilateral salpingectomy and bilateral oophorectomy. A post-menopausal state is defined as no menses for 12 months without an alternative medical cause and confirmed by a follicle stimulating hormone (FSH) result of  $\geq 40$  IU/L.

---

#### **9.4.1 Sperm Donation**

Men should not donate sperm from the time of informed consent until 175 days after last IMP administration (approximately 2.5 sperm turnover rate).

#### **9.4.2 Egg Donation**

Women should not participate in egg donation from dosing, from the time of informed consent until 115 days after last IMP administration.

### **9.5 Pregnancy**

Subjects will be instructed that if they/their partner becomes pregnant during the study this should be reported to the investigator. The investigator should also be notified of pregnancy occurring during the study but confirmed after completion of the study. In the event that a subject/subject's partner is subsequently found to be pregnant after the subject is included in the study, then consent will be sought from the subject/partner and, if granted, any pregnancy will be followed and the status of mother and/or child(ren) will be reported to the Sponsor after delivery. Any subject reporting a pregnancy during the study will be discontinued from study treatment and every reasonable effort will be made by Quotient to follow up the pregnancy until delivery.

A pregnancy notification form and follow-up will be completed.

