### 6.3 Population Rationale

As this is a Phase I study assessing the PK, PD, tolerability and safety of PDM608, the most relevant population is healthy volunteers. Subjects who are non-smokers without a history of alcohol, drug abuse or regular co-medication are proposed to avoid interaction on drug metabolism and noncompliance.

It is not known whether PDM608 can cause fetal harm when administered to pregnant women, affect male or female fertility, or whether it is secreted in human milk. Therefore, women of childbearing potential will not be enrolled in this study, men will be allowed to participate as long as they comply with the contraception requirements as detailed in [Section 9.4](#), and men with pregnant partners will be excluded from the study (see [Section 9.3](#)).

Based on the above considerations and target population, healthy non-pregnant and non-lactating women of non-childbearing potential (WONCBP) and healthy men aged 18 to 65 years are considered suitable subjects for this study. GM-CSF preparations have previously been studied in healthy volunteers (Lane 1995; Fishmeister 1999).

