### 10.3.6 Follow-up

If a subject reports any AEs that can present a cause for concern, they will be required to attend the clinical unit for a further follow-up assessment (as an unscheduled visit) and will be followed up until the AE has resolved. Completion of the last scheduled return visit or unscheduled follow-up call/visit will be considered the end of the study.

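### Section 9.5 asks subjects to report only pregnancies arising during the study, while Section 9.4 keeps men on contraception until 175 days after the last dose, so no instruction covers partner pregnancies in the later part of that period

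*Combined protocol and SAP*

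**What the plan says.** Four parts of the protocol bear on this.

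- **Reporting (Section 9.5).** The instruction to subjects is "Subjects will be instructed that if they/their partner becomes pregnant during the study this should be reported to the investigator". The next sentence adds: "The investigator should also be notified of pregnancy occurring during the study but confirmed after completion of the study". A third sentence, with no end date, says that if a subject or partner is later found to be pregnant, consent will be sought, the pregnancy followed, and its status reported to the Sponsor after delivery.
- **Male restrictions (Section 9.4 and 9.4.1).** Men with partners of childbearing potential must use a condom plus "highly effective contraception from the time of informed consent until 175 days after last IMP administration". Men with other partners are "required to use a condom from the time of informed consent until 175 days after last IMP administration". The sperm donation restriction ends at the same point: "Men should not donate sperm from the time of informed consent until 175 days after last IMP administration". Inclusion criterion 4 makes agreement to adequate contraception an entry condition.
- **Reason (Section 6.3).** "It is not known whether PDM608 can cause fetal harm when administered to pregnant women, affect male or female fertility".
- **End of study.** Section 10.3.6 states: "Completion of the last scheduled return visit or unscheduled follow-up call/visit will be considered the end of the study". Section 17.5 defines the end of the study at trial level, by the last follow-up of the final subject or a Sponsor decision. Section 9.5 does not say which meaning applies.

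**The concern.** The protocol declares a period in which a man's exposure might matter to a partner or pregnancy, and runs it to 175 days after the last dose. The reporting instruction is tied instead to the study. The second sentence of Section 9.5 moves only the date on which a pregnancy may be confirmed; the pregnancy must still have occurred during the study.

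For a first-in-human product whose fetal and fertility effects are stated to be unknown, a partner pregnancy conceived within the protocol's own period is what the safety record should capture. The subject is the natural source of that information, and for much of the period the protocol does not ask him for it. Completeness of the pregnancy data then rests on chance reports.

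**Working it through.** The 175 days is a rule, not a derived figure, so there is no calculation of the plan's to reproduce for it. The check is calendar arithmetic.

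**Inputs**

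- Contraception period after last dose: 175 days (Section 9.4).
- Part 1: single dose on Day 1; last return visit Day 22, at 504 h, or 504/24 = 21 days after dosing (Appendix 2).
- Part 2: Dose 4 on Day 22; last return visit Day 60, at 912 h, or 912/24 = 38 days after Dose 4 (Appendix 3).
- Window for these visits: ±24 h. Screening: Day -28 to Day -2.
- AE collection: until 30 days after the last dose (Sections 13.1 and 13.3).

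Check on the visit days: from Day -28 to Day 22 is 28 + 21 = 49 days, or 7.0 weeks, matching the synopsis for Part 1. From Day -28 to Day 60 is 28 + 59 = 87 days, or 12.4 weeks, against a stated estimate of 13. That difference does not affect the point.

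**Subject-level end of study (Section 10.3.6)**

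Uncovered days = 175 - (last visit day - last dose day).

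| | Uncovered days | Share of 175 | Range with ±24 h | Share of whole period from consent |
|---|---|---|---|---|
| Part 1 | 175 - (22 - 1) = 154 | 88% | 153 to 155 days | 154/203 to 154/177 = 76% to 87% |
| Part 2 | 175 - (60 - 22) = 137 | 78% | 136 to 138 days | 137/224 to 137/198 = 61% to 69% |

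The whole-period denominators add screening (28 or 2 days) and, in Part 2, the 21 days from Dose 1 to Dose 4: 28 + 175 = 203 and 2 + 175 = 177; 28 + 21 + 175 = 224 and 2 + 21 + 175 = 198.

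If the 30-day AE window were taken as the limit instead, 175 - 30 = 145 days (83%) would be uncovered in either part.

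**Trial-level end of study (Section 17.5)**

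The documents give no calendar, so this is an illustration. Assumptions: no recruitment or review delay, SAD cohorts run back to back, MAD starts straight after SAD Cohort 3, and exactly three MAD cohorts are dosed.

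- Each SAD cohort takes 72 h for the sentinels plus 96 h for the main group, about 7 days. Three cohorts take 21 days.
- Each later MAD cohort waits for Day 26 data, 25 days after Dose 1. MAD cohorts start on days 21, 46 and 71 after the first SAD dose.
- MAD Cohort 3 reaches its Day 60 visit on day 71 + 59 = 130, taken as the end of the trial.

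Uncovered days = (day of last dose + 175) - 130.

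| Cohort | Day of last dose | Uncovered days | Share of 175 |
|---|---|---|---|
| SAD 1, main group | 3 | 48 | 27% |
| SAD 3, main group | 17 | 62 | 35% |
| SAD 5, main group | 31 | 76 | 43% |
| MAD 1 | 42 | 87 | 50% |
| MAD 2 | 67 | 112 | 64% |
| MAD 3 (final) | 92 | 137 | 78% |

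Later MAD timelines would shrink the early-cohort gaps. An early end to the trial, or SAD Cohorts 4 and 5 running late relative to MAD, would widen some of them. The final MAD cohort's 137 days does not depend on the timetable.

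**Other routes**

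No visit is scheduled after Day 22 in Part 1 or Day 60 in Part 2. Section 13.4.1 lists a congenital anomaly as an SAE, and Section 15.1 allows expedited reporting of some SAEs after a subject has completed the study. Both need someone to learn of the pregnancy first.

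**The case against.** The strongest reply is that the gap depends on an undefined term. Section 17.5 is the section headed as the declaration of the end of the study, Section 8.3 has a separate term for subject completion, and the wording in Section 10.3.6 resembles that of Section 17.5. On the trial-level reading, the illustration above leaves less than half of the 175 days uncovered for every SAD cohort. This stands: 88% and 78% belong to one reading and should not be given without the other. It does not remove the gap for men in the last cohorts, and having two available readings is itself a reason to define the term. The subject-level reading has some support, because Section 10.3.6 concerns an individual's follow-up, and Section 9.6 names a period after the last dose separately from study duration when it wants one.

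A reader might infer that these pregnancies go unreported and their outcomes are lost. The documents do not support that. The third sentence of Section 9.5 has no end date, so a later pregnancy that becomes known would be followed and reported to the Sponsor. What is missing is an instruction that would make it known.

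A reader might also infer that most participants will be men, because women of childbearing potential are excluded. The documents give no figure, and post-menopausal or sterile women up to age 65 are eligible. The point does not need that premise. Events are likely to be few: men with partners of childbearing potential must use two methods, and a quarter of each cohort receives placebo (2 of 8; 3 of 12).

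Finally, the consent pages are not in the reviewed copy, so the wording given to subjects there cannot be checked. It may already cover the full period; the protocol text does not.

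**Conclusion.** The mismatch is real. On the subject-level reading, no instruction prompts a report of a partner pregnancy conceived in the last 154 of 175 post-dose days in Part 1 or 137 of 175 in Part 2. On the trial-level reading, the gap is smaller for earlier cohorts, by an amount that depends on a timetable the documents do not give, and remains about 137 days for men in a final MAD cohort. Both results take the last visits as scheduled, with no later unscheduled contact.

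The conclusion concerns the absence of a request to report. It does not say that later pregnancies would be refused, ignored or left without follow-up, and it takes no view on whether 175 days is the right contraception period. The change is worth making before enrolment: it bears on the completeness of safety data about a risk that the protocol calls unknown, and it is a matter of wording.

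**What to change.** Reconcile Section 9.5 with Section 9.4. Male subjects should be instructed to report any partner pregnancy occurring from informed consent until the end of the contraception period set in Section 9.4. Referring to that section, rather than repeating a number, keeps the two aligned if the period is amended.

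Two details matter. The start should be informed consent, as in Section 9.4; starting at first dose would drop pregnancies between consent and dosing. The extension should apply to male subjects only, because Section 9.4 sets no contraception period for the women eligible here; leave the instruction for female subjects' own pregnancies unchanged. Carry the wording into the discharge instructions, and check that the consent form agrees.

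The cost is a protocol edit, with a consent edit if needed. The site and pharmacovigilance provider must accept a few spontaneous reports after the last visit. No visit or test is added.
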